# **Nasal high frequency oscillation ventilation versus nCPAP to reduce post-extubation pCO2 in very low birth weight infants: a randomized controlled trial**

## **Objectives**

To investigate whether nasal high frequency oscillation ventilation (nHFOV) immediately after extubation reduces the paCO2 in comparison with nasal continuous positive airway pressure (nCPAP) at 72 hours after extubation in very low birth weight infants (VLBWs).

## **Protocol/Methods**

### **1. Trial design**

Randomized controlled clinical trial of nHFOV versus nCPAP immediately after extubation.

### **2. Participants**

#### Eligibility criteria

- Gestational age <32+0 weeks
- Birth weight <1500 g
- Received mechanical ventilation via an endotracheal tube for  $\geq 120$  h
- Caffeine treatment according to unit guidelines
- Arrival at the preset extubation criteria:
  - Time-cycled, pressure-controlled ventilation:  
PIP  $\leq 22$  cm H2O, PEEP  $\leq 6$  cm H2O,  
FiO2 25-40% to maintain SpO2 at 90-94%.  
paCO2 <65 mmHg with pH >7.2
  - Volume guarantee ventilation:  
Working Ppeak  $\leq 22$  cm H2O, PEEP  $\leq 6$  cm H2O  
FiO2 25-40% to maintain SpO2 at 90-94%.  
paCO2 <65 mmHg with pH >7.2
  - High frequency oscillation ventilation: set Pmean  $\leq 12$  cm H2O, Amplitude  $\leq 30$  cm H2O  
FiO2 25-40% to maintain SpO2 at 90-94%.  
paCO2 <65 mmHg with pH >7.2
- Decision of the attending clinician to extubate

#### Exclusion criteria

- Major congenital malformation requiring surgery (e.g. esophageal atresia, diaphragmatic hernia, abdominal wall defect)
- Duct-dependent congenital heart disease
- Neuromuscular disease
- Participation in another RCT
- Death before reaching the eligibility criteria
- Hydrocortisone treatment at the time of enrolment
- Chronological age >28 days

### **3. Study settings**

Two universitarian tertiary neonatal intensive care units in Berlin.

#### 4. Intervention

Application of nHFOV or nCPAP immediately after extubation from endotracheal HFOV or from conventional ventilation.

- Equipment:
  - Devices used for endotracheal ventilation, nHFOV and nCPAP: Leoni Plus (Heinen und Löwenstein, Germany) or VN 500 (Dräger, Germany)
  - Interfaces: Endotracheal tubes (VYGON, France; Portex, Smiths Medical, UK) for endotracheal ventilation. Binasal prongs (Fisher & Paykel, New Zealand) for nHFOV and nCPAP.
  - Humidifier: MR 850 AGU (Fisher & Paykel, New Zealand)
- Primary intervention:
  - Extubation by withdrawing the endotracheal tube without sustained inflation
  - nHFOV group: immediately after extubation, apply nHFOV via binasal prongs. Set frequency at 10 Hz, I:E ratio 33:66, Amplitude 20 cm H2O, Pm 8 cm H2O, flow automatic (7 l/min). Set FiO2 to maintain SpO2 at 90-94%.
  - nCPAP group: immediately after extubation, apply nCPAP via binasal prongs. Set CPAP level at 8 cm H2O, flow 7 l/min. Set FiO2 to maintain SpO2 at 90-94%.
- Weaning of non-invasive respiratory support:
  - The weaning process is left to the discretion of the attending physician.
  - Once the infant is considered stable on nHFOV, intermittent or permanent weaning to nCPAP is allowed.
  - Once the infant is considered stable on nCPAP, intermittent or permanent weaning to high flow nasal cannula is allowed.
- Increasing non-invasive respiratory support:
  - Increasing non-invasive respiratory support is left to the discretion of the attending physician. The following settings are allowed in the nHFOV- and nCPAP-group, respectively.
  - nHFOV group:
    - Maximum amplitude 30 cm H2O, minimum frequency 9 Hz.
    - Maximum set Pmean 8 cm H2O.
  - nCPAP group:
    - Maximum CPAP level 8 cm H2O, maximum flow 8 l/min.
- Definition of treatment failure (infant meets at least one criterion):
  - Sustained pCO2 >80 mmHg and pH <7.20 confirmed by arterial or capillary blood gas analysis in spite of optimized non-invasive respiratory support with maximum settings as defined above.
  - FiO2 >0.6 to maintain SpO2 at 90-94% in spite of optimized non-invasive respiratory support with maximum settings as defined above.
- Reintubation:
  - Study patients may be intubated at any time due to clinical considerations (with or without reaching a criterion of "treatment failure", as defined above).
- "Rescue-nHFOV" for infants in the nCPAP-group who "fail" nCPAP (defined as reaching a criterion of "treatment failure", as defined above), but do not need immediate reintubation:
  - Trial of nHFOV via binasal prongs.
  - Choice of nHFOV settings are at the discretion of the attending clinician.
- "Rescue treatment" for infants in the nHFOV-group who "fail" nHFOV (defined as reaching a criterion of "treatment failure", as defined above), but do not need immediate reintubation:

- Choice of non-invasive respiratory support for the “rescue treatment” (e.g. nIPPV, nHFOV) and ventilator settings are at the discretion of the attending clinician.
- Planned data collection to document the respiratory support provided in the nCPAP- and the nHFOV-group:
  - Blood gas result before extubation (pH, paO2, paCO2 and BE).
  - Ventilator settings before extubation (mode and FiO2 in all patients; set Pmean during HFO; PIP and PEEP during time-cycled, pressure-controlled ventilation; working Ppeak and PEEP during volume guarantee ventilation).
  - Documentation of non-invasive respiratory support, including settings of nHFOV and/or nCPAP every 24h during the first 3 days after extubation and at 7 days after extubation (mode, set mean nHFOV pressure, frequency, amplitude; CPAP level; flow, FiO2), and after switch to “rescue treatment” or ”rescue-nHFOV”, if applicable.

## 5. Outcomes

- Primary outcome:
  - paCO2 at 72 h (timeframe: 64 h to 80 h) after extubation
- Secondary outcomes:
  - pH, paO2, paCO2, BE at 2 h (timeframe: within first 6 h) after extubation
  - pH, paO2, BE at 72 h (timeframe: 64 h to 80 h) after extubation
  - Successful extubation (defined as spontaneous breathing in the assigned treatment group for  $\geq 72$ h without being reintubated or reaching the criterion of “treatment failure”, as defined above)
  - Treatment failure (defined as reaching the criterion of “treatment failure”, as defined above, within the first 7 days after extubation)
  - Reintubation within the first 7 days after extubation
  - Adverse effects observed after extubation: documented episodes of airway obstruction due to highly viscous secretions, IVH IIIo-IVo (Papile), surgical NEC, pneumothorax, pulmonary interstitial emphysema, mild BPD (Jobe), PDA requiring surgical closure, ROP requiring laser treatment and/or injection of bevacizumab, PVL
  - Respiratory support: total duration of mechanical ventilation, total duration of supplemental oxygen, number of infants discharged with home oxygen
- Additional secondary outcomes for those infants who received “rescue treatment”:
  - pH, paO2, paCO2, BE at 2 h (timeframe: within first 6 h) after switch to “rescue” therapy
  - Successful rescue (defined as spontaneous breathing for  $\geq 72$ h after starting “rescue” therapy, without reaching the criterion of “treatment failure”, as defined above)
- Follow-up study:
  - Lung function testing at 52 weeks’ corrected gestational age.

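### Does the 7-day treatment-failure outcome need a composite with reintubation, given that infants may be reintubated without meeting a failure criterion?

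*Combined protocol and SAP*

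**What the plan says.** Section 4 (Intervention) defines treatment failure by physiology alone: either sustained pCO2 above 80 mmHg together with pH below 7.20, or an FiO2 above 0.6 to hold the saturation target. Each applies only "in spite of optimized non-invasive respiratory support with maximum settings as defined above". Reintubation is not part of the definition. The reintubation rule in the same section reads "Study patients may be intubated at any time due to clinical considerations (with or without reaching a criterion of" treatment failure).

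Section 5 (Outcomes) then lists three related secondary outcomes:

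- The 7-day failure outcome, "Treatment failure (defined as reaching the criterion of" treatment failure, which uses the Section 4 criteria.
- Reintubation in the same 7 days, with no restriction on the reason.
- Successful extubation, which requires at least 72 h of spontaneous breathing on the assigned support "without being reintubated or reaching the criterion of" treatment failure.

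The room to escalate before settings count as maximal differs between arms. For nCPAP the starting instruction is "Set CPAP level at 8 cm" H2O, which is already the ceiling, so only flow can rise, from 7 l/min to the "maximum flow 8 l/min". For nHFOV the amplitude can go from 20 to 30 cm H2O, and the frequency can fall from 10 Hz to the "minimum frequency 9 Hz". Respiratory-support settings are to be recorded "every 24h during the first 3 days after extubation and at 7 days after extubation", and after any switch to rescue support.

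**The concern.** An infant reintubated on day 5 on clinical grounds, with neither criterion met, has plainly not done well on non-invasive support, yet counts as a non-failure in the 7-day failure outcome. Reintubation also takes the infant off the support on which the criterion is judged, so it acts as a competing event. An arm with more early discretionary reintubation could therefore show fewer treatment failures. Reintubation is at the clinician's discretion, the plan describes no blinding, and maximal settings are reached by different steps in the two arms, so a distorted comparison is conceivable.

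The two events are joined explicitly only at 72 h. After that a reader would have two separate 7-day rates, and these cannot be combined without knowing how many infants had both events. What is at stake is the interpretation of one secondary outcome.

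**Working it through.** **The plan's own figures.** No rate is given for either 7-day outcome. The only event rate is in Section 6: 21% reintubated within 72 h, with 28 infants per arm. That sample size is for paCO2. The SD is not stated; an assumed SD of 8.1 to 8.2 mmHg gives 22 evaluable infants per arm, and 22 / 0.79 = 27.8, rounded up to 28. The definition of treatment failure does not enter this calculation.

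**Where each type of infant is counted**

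| Infant | 7-day failure | 7-day reintubation | Successful at 72 h |
|---|---|---|---|
| Criterion met by 72 h, not reintubated | yes | no | no |
| Reintubated by 72 h, no criterion | no | yes | no |
| First event is reintubation between 72 h and day 7, no criterion | no | yes | not excluded by this event |
| Both events by 72 h | yes | yes | no |

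No reintubated infant disappears from the outcomes. Only the third row is both absent from the failure outcome and not made unsuccessful at 72 h by the event, and that row is counted under 7-day reintubation.

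**Up to 72 h.** Let u be the share of reintubated infants who met no criterion (not given; assumed 0 to 100%). Infants per arm missing from the criterion outcome = 28 × 0.21 × u = 5.88u:

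- u = 0: 0
- u = 25%: 1.47
- u = 50%: 2.94
- u = 75%: 4.41
- u = 100%: 5.88

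All of them are already unsuccessful in the 72 h outcome. These are upper values, because an infant re-extubated and later meeting a criterion would be counted.

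**72 h to day 7.** Let r be the share first reintubated in this period (not given; assumed 0 to 15%). Infants per arm = 28 × r × u:

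| r | u = 50% | u = 100% |
|---|---|---|
| 0% | 0 | 0 |
| 5% | 0.7 | 1.4 |
| 10% | 1.4 | 2.8 |
| 15% | 2.1 | 4.2 |

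**Overlap.** With F infants meeting a criterion and R reintubated, the number with either event lies between max(F, R) and F + R. With F = 6 and R = 8 of 28 (assumed), that is 8 to 14 infants, or 8/28 = 29% to 14/28 = 50%. This uncertainty faces a reader who sees only the two totals. The trial team holds both outcomes for each infant and can count the overlap directly.

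**Would a composite cure the suspected distortion?** It would keep the same criterion, with its arm-specific escalation steps, and add discretionary reintubation. Both suspected sources of bias would remain.

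**Would it add power?** For two proportions with n = 28 per arm, power = Φ{(|p1 − p2| − 1.96 √[2p̄(1 − p̄)/n]) / √[(p1(1 − p1) + p2(1 − p2))/n]}, where p̄ is the mean of p1 and p2. For assumed composite rates of 40% against 20%:

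- 1.96 √(2 × 0.3 × 0.7/28) = 0.240
- √[(0.24 + 0.16)/28] = 0.1195
- power = Φ[(0.20 − 0.240)/0.1195] = Φ(−0.335) = 0.37

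For 50% against 25% the same formula gives 0.49. At this trial size the composite would be descriptive, and a cross-table serves that purpose as well.

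**The case for a change.** The best argument for a change is that a separate reintubation outcome does not undo the competing event. Suppose one arm has F = 3 and R = 6 and the other F = 6 and R = 3. The two outcomes then point in opposite directions, and each arm's combined count could be anything from 6 to 9. Only the overlap settles it, and a composite chosen after seeing the results would be post hoc. The addition needs no further patients.

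The mechanism stands: the failure outcome should not be read without the reintubation outcome beside it. But the plan places those two outcomes next to each other, and opposite directions in them would themselves alert the reader. A table of criterion only, reintubation only, both and neither describes planned outcomes and does not depend on prespecifying a new hypothesis. One caution applies: identifying infants reintubated before any criterion requires the order of events, because an infant who is reintubated, re-extubated and then meets a criterion falls under both. Each outcome is tied to a window counted from extubation, so the timing of events has to be established in any case.

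A second argument is that, apart from records after a switch to rescue, no settings record is scheduled between day 3 and day 7, so the use of maximal settings could not be checked there. This carries little weight. The schedule is presented as documentation of the support given, not as the way failure is ascertained. A once-daily snapshot before 72 h would not show the settings at the moment of an event either.

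**Conclusion.** The reading of the text is correct, but no change to the plan follows. The failure outcome measures what its definition says, a physiological criterion. The discretionary event is reported separately over the same 7 days, and the two are brought together at 72 h. Following the plan as written gives no wrong result.

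Up to 72 h, between 0 and 5.9 infants per arm could be absent from the criterion outcome, and all of them are captured elsewhere. From 72 h to day 7 the range is 0 to 4.2 per arm under assumed reintubation of up to 15%, and these infants are captured in the reintubation outcome. The documents support neither a size nor a direction for any between-arm effect; with equal reintubation and an equal share without a criterion, the omission is the same in both arms. The primary outcome and the 28 per arm do not depend on this point.

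The conclusion rests on both 7-day outcomes being reported by arm, as listed. Analysts who want the combined picture can add the four-way table, with the order of events, as a supportive display when results are written up.

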**10. Randomization: allocation concealment mechanism**

Sequentially numbered opaque sealed envelopes. Patients are randomized immediately before extubation.

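### Airway obstruction rests on unprompted chart entries by staff who appear to know the arm, and its unit is not fixed, so an arm difference could partly reflect unequal charting

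*Combined protocol and SAP*

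**What the plan says.** Section 5 (Outcomes) gives a list of secondary outcomes introduced as "Adverse effects observed after extubation". The first item is "documented episodes of airway obstruction due to highly viscous secretions". Nothing states what counts as an episode, who decides, when the infant is checked, when the window closes, or whether episodes or affected infants are analysed. No analysis method is given for any adverse effect.

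The design is stated in section 1 as "Randomized controlled clinical trial of nHFOV versus nCPAP immediately after extubation". Blinding of bedside staff, assessors or data collectors is not mentioned anywhere. Section 10 relies on "Sequentially numbered opaque sealed envelopes", which conceal the allocation only until it is made.

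Section 4 (Intervention) has a list headed "Planned data collection to document the respiratory support provided in the nCPAP- and the nHFOV-group". It covers blood gas and ventilator settings before extubation, then mode and settings "every 24h during the first 3 days after extubation and at 7 days after extubation" and after a switch to rescue. Obstruction is not on it.

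Section 4 also lets infants change mode. In the nHFOV group, "intermittent or permanent weaning to nCPAP is allowed" once the infant is stable. An infant who fails nCPAP without needing immediate reintubation may have a "Trial of nHFOV via binasal prongs". Nothing says to which arm or mode an episode after a switch belongs.

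**The concern.** To enter the data, an episode must be noticed, written down and attributed to secretions. All three steps appear to fall to people who can see which mode the infant is on, since the two modes have different settings managed at the bedside. If the habit of charting differs between arms, the comparison picks up that difference along with any real one. It can create an apparent harm or hide a true one.

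The contrast with the rest of the list makes this item stand out. Five of the eight other adverse effects are tied to a grading system or a procedure or treatment: IVH, NEC, BPD, PDA and ROP. Treatment failure and reintubation have a 7-day window. Obstruction is the only item defined by documentation and worded in episodes.

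The wording raises a second issue. Episodes can recur in an infant, but infants were randomised. A comparison of episode totals that treats them as independent would overstate the precision.

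Section 7 has the secondary endpoints analysed at half enrolment as well, when a few infants would weigh most.

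**Working it through.** **Inputs.** From the documents: 28 infants per arm (section 6). Every event rate, charting rate and degree of clustering below is an assumption, because the plan gives none.

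**The plan's own figure.** No figure is stated for obstruction. The 28 per arm is for paCO2 and cannot be reproduced, because the SD is not given. It is consistent with an SD of about 8.25 mmHg: 22 evaluable per arm, and 22/(1 − 0.21) = 27.8, rounded up to 28. It serves here only as the sample size.

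**Step 1: unequal charting, no true difference, infants as the unit.** Observed rate = true rate × proportion charted. The false-positive rate is the exact probability that a two-sided Fisher test on 28 v 28 gives p < 0.05.

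| True rate, both arms | Charted | Observed | False positives |
|---|---|---|---|
| 20% | 100% v 100% | 20% v 20% | 2.0% |
| 20% | 80% v 50% | 0.20×0.80 = 16% v 0.20×0.50 = 10% | 3.4% |
| 20% | 90% v 50% | 18% v 10% | 5.4% |
| 30% | 90% v 50% | 27% v 15% | 11.2% |
| 50% | 90% v 70% | 45% v 35% | 7.2% |
| 50% | 90% v 50% | 45% v 25% | 26.3% |

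In the second row the expected counts are 28×0.16 = 4.5 and 28×0.10 = 2.8 infants. A result of 5 v 3 gives p = 0.70.

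**Step 2: unequal charting that hides a difference.** For a true 50% v 15%, power with full charting is 75.2%. If the higher-rate arm is charted at 60%, its observed rate is 0.50×0.60 = 30%, and power against 15% is 17.1%. For a true 40% v 10%, the same loss (40% becomes 24%) takes power from 66% to 16%.

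**Step 3: repeat episodes, only if totals were tested as independent.** Negative-binomial episodes with mean m and dispersion k have variance/mean = 1 + m/k. The simulation used m = 1, no true difference, 28 per arm and 40,000 replicates, with an exact conditional binomial test on the totals.

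| k | Variance/mean | Episode-total test | Infant-level Fisher |
|---|---|---|---|
| no clustering | 1 | 3.7% | 2.9% |
| 1 | 2 | 13.7% | 2.3% |
| 0.5 | 3 | 22.4% | 2.5% |
| 0.25 | 5 | 34.5% | 2.7% |

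For k = 0.5 the normal approximation gives 2×(1 − Φ(1.96/√3)) = 25.8%, somewhat above the simulated value. As an illustration, 5 v 5 affected infants gives p = 1.00. If repeats make those same infants contribute 5 v 16 episodes, the test on totals gives p = 0.027.

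Steps 1 and 3 do not describe one population. Mean 1 with k = 0.5 implies 1 − (1/3)^0.5 = 42% of infants affected, not 20%.

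**Step 4: what changing the unit achieves.** Counting infants removes the problem in step 3. It does not remove the one in step 1, where infants are already the unit and the rate still reaches 26.3%. Ascertainment has to be made the same in both arms as well.

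**The case against.** The strongest reply is that the plan commits to none of the analyses that would go badly wrong. A reader might infer that episodes are the unit and will be tested as independent, with an error rate near 26%. The documents do not support that: no unit is fixed and no test is named. The other adverse effects are naturally yes/no per infant, so a count of infants with a documented episode is an equally fair reading. The clustering figures are therefore conditional.

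A reader might also infer that nHFOV infants will be charted more alertly because the mode is new. Nothing in the documents shows this; unequal charting is possible, and its direction is unknown. That the trial is open-label is itself an inference from the absence of any blinding.

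The section 4 list is about respiratory support and is not a full case report form. It omits the other adverse effects too, so it does not prove that obstruction goes unchecked. Small charting gaps also do little at infant level in a trial of this size.

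These points stand, and they narrow the concern without answering it. The plan still makes documentation and a causal judgement the route into the data, and describes no check common to both arms.

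**Conclusion.** The concern holds in a limited form. As written, a difference in airway obstruction could partly reflect unequal charting, and if episode totals were compared as independent the precision would be overstated. At infant level with 28 per arm, the charting effect runs from negligible (3.4% false positives, a true 20% charted at 80% v 50%) to material (26%, a true 50% charted at 90% v 50%; or power down from 75% to 17%). All of this rests on assumed rates: it shows what can happen, not that it will. One secondary adverse effect is affected, and the primary paCO2 outcome is not. It is a minor point, worth making because the remedy is cheap.

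**What to change.** At each support record already scheduled in section 4 (24, 48 and 72 h and day 7), put the same yes/no question in both arms: has there been any airway obstruction since the last record that led to a recorded, non-routine intervention? State that routine suctioning does not count. Define the outcome as the number of infants with at least one such event by day 7, which matches the window for treatment failure and reintubation. Compare it by randomised arm, whatever mode the infant was on at the time. List episode counts per infant descriptively, without a test.

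The cost is one tick-box at four time points. Events after day 7 would be reported only descriptively, and the day-7 box looks back four days, so it still leans on notes or recall. The same unblinded staff would answer, so the change reduces charting bias and does not remove it. It does make an explicit no distinguishable from a missing entry.

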## 6. Sample size

Assuming a variability of the paCO2 as previously reported for difficult-to-wean preterm infants in our unit (Czernik C, *J Matern Fetal Neonatal Med* 2012) and a reintubation rate of 21% within 72 h after extubation, we calculated a sample size of 28 patients in each study arm to detect a difference in the paCO2 of 7 mmHg between the study groups, using a two-sided significance of 0.05 and a power of 0.8.

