**7. Interim analyses and stopping guidelines**

An independent statistician performs an interim-analysis on the primary and secondary endpoints once 50% of the patients are randomized and outcome data is available.

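### Does the 21% reintubation allowance leave the primary paCO2 comparison undefined?

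*Combined protocol and SAP*

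**What the plan says.** Section 6 (Sample size) lists four ingredients. The first is a paCO2 variability, cited from an earlier report of the unit but not given as a number. The second is the reintubation assumption, "a reintubation rate of 21% within 72 h after extubation, we calculated a sample size of 28 patients in each study arm". The third is the target, "to detect a difference in the paCO 2 of 7 mmHg between the study groups", and the fourth the error rates, "using a two-sided significance of 0.05 and a power of 0.8". How the 21% enters is not stated.

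Section 5 (Outcomes) defines the primary outcome as paCO2 "at 72 h (timeframe: 64 h to 80 h) after extubation", with no condition on the support the infant is then receiving. A secondary outcome in the same list does carry one: "Successful extubation (defined as spontaneous breathing in the assigned treatment group for" at least 72 h, with neither reintubation nor treatment failure. Reintubation and treatment failure within 7 days are also separate secondary outcomes.

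Section 4 (Intervention) makes a sustained high pCO2 one route to treatment failure (above 80 mmHg with "pH <7.20 confirmed by arterial or capillary blood gas analysis"). It also leaves reintubation open on other grounds: "Study patients may be intubated at any time due to clinical considerations".

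Section 7 plans an "interim-analysis on the primary and secondary endpoints once 50% of the patients are randomized and outcome data is available". No section gives an analysis population, a primary test or a missing-data rule.

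**The concern.** A reintubation rate usually enters a comparison of two means as loss of evaluable patients. If that was intended, the authors expected to drop reintubated infants, whereas Section 5 read literally keeps them. The two choices answer different questions. Dropping them conditions the comparison on an event after randomisation that is linked to paCO2 and may be affected by treatment. Keeping them brings in gases taken on a ventilator, which can dilute the contrast and hide failure.

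At 21%, about 6 of 28 infants per arm (0.21 × 28 = 5.9), or about 12 of 56, would be concerned. The interim look covers about 28 infants, again with about 6 reintubated. A rule not settled by then could be chosen with outcome data in hand.

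**Working it through.** **Inputs.** From Section 6: difference 7 mmHg, two-sided alpha 0.05, power 0.80, 28 per arm, 21% reintubated within 72 h. Assumed, because the documents do not give them: the SD, the correlation ρ between paCO2 and the tendency to be reintubated, and the gases seen on a ventilator.

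**1. Can 28 be reproduced?** Not directly, because no SD is given. It can only be solved backwards, with SD = 7 / [(1.960 + 0.842) × √(2/n)].

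- 21% as attrition: 28 × 0.79 = 22.1 evaluable, and 22/0.79 = 27.85, rounded up to 28. With n = 22 the SD is 8.29 (8.10 from the exact t-test).
- No allowance: with n = 28 the SD is 9.35 (9.18 from the t-test).

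**2. Does the match at 22/0.79 show that reintubated infants were to be excluded?** Only weakly. The 22 was found by working back from 28. Of the 15 integers from 23 to 37, 12 can be written as some n/0.79 rounded up (all except 24, 29 and 34), so a match was likely in any case. A different inflation also gives 28: 23 × 1.21 = 27.8.

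**3. What would the choice do to power?** Illustration with SD 8.1, a true difference of 7 mmHg and 28 randomised per arm. Infants above a common threshold on a latent variable, correlated ρ with paCO2, are reintubated before the gas; the overall rate is 21%. *Left out* uses the remaining infants. *Kept* replaces the reintubated infants' gases by values with the same mean in both arms, midway between the arm means, and SD 8.1. Power is from the noncentral t.

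| ρ | Reintubated, nCPAP / nHFOV | Left out: difference, power | Kept: difference, power |
|---|---|---|---|
| 0 | 21% / 21% | 7.00, 0.80 | 5.53, 0.70 |
| 0.3 | 25% / 17% | 6.73, 0.79 | 5.38, 0.69 |
| 0.5 | 27% / 15% | 6.26, 0.75 | 5.13, 0.67 |
| 0.7 | 29% / 13% | 5.57, 0.70 | 4.75, 0.64 |

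At ρ = 0 the kept difference is 7 × 0.79 = 5.53. If all 28 per arm kept the full 7 mmHg, power would be 0.89. With SD 9.18 and ρ from 0 to 0.5, power is 0.70 to 0.65 left out and 0.59 to 0.56 kept.

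**4. How large could the selection bias be if paCO2 is unaffected?** Suppose reintubation is 27% on nCPAP and 15% on nHFOV. Leaving these infants out lowers each arm's mean by ρ × SD × φ(c)/Φ(c), where c is the cut-off for that arm's rate. The ratio is 0.4529 at 27% and 0.2743 at 15%, so the bias is ρ × 8.1 × 0.1786 = 1.45ρ. That is 0.43, 0.72 and 1.01 mmHg at ρ = 0.3, 0.5 and 0.7, or about 6%, 10% and 14% of the 7 mmHg target. With SD 9.18 and ρ = 0.5 it is 0.82 mmHg. In this example it makes nHFOV look worse.

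**5. Section 5 beside Section 6.** The authors wrote a no-reintubation condition into successful extubation and none into the primary gas a few lines above. Section 6 mentions reintubation as a planning figure only. Nothing in it contradicts Section 5.

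**The case for a change.** The strongest case for a change is that a trial of 56 infants should not leave the status of about 12 of them to be settled later, particularly with an interim analysis of the primary endpoint halfway. The event is foreseen, is linked to the outcome, and moves power from 0.80 to 0.70 even at ρ = 0. Writing the rule down would need no new measurement.

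Part of this stands. The population and the handling of gases after reintubation are not written, and neither is the handling of deaths or missing gases. One sentence, together with the SD and the role of the 21%, would make the plan easier to check, and is best settled before the interim look.

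The rest does not require an amendment. The core of the proposed rule, assigned arm and observed gas whatever the support, is what Section 5 already says when read with a randomised design. A comparison of infants still on non-invasive support would be a recognised, though selection-prone, answer to the physiological objective. Preferring one is a choice of question. Keeping all infants has its own price: in the illustration 80% power would need about 36 per arm at ρ = 0 and 38 at ρ = 0.5. Section 4 records respiratory support every 24 h for the first 3 days, and Section 5 reports reintubation and treatment failure separately. Failures hidden by ventilator gases would therefore show elsewhere in the results, and a supportive analysis of non-reintubated infants needs no extra data.

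**Conclusion.** No change to the plan follows. This is an unwritten rule that analysts can fill sensibly from Section 5, combined with a fair trade-off between two questions. Sections 5 and 6 are not in conflict: exclusion of reintubated infants is an inference from an unexplained planning figure, and the arithmetic supporting it would have fitted most sample sizes of this order.

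As to size, in the SD 8.1 illustration the two readings differ by about 0.06 to 0.10 in power across ρ from 0 to 0.7, and the exclusion bias with no paCO2 effect is about 0.4 to 1.0 mmHg for ρ from 0.3 to 0.7. These figures rest on the assumed SD, ρ, ventilator gases and reintubation split, and on all reintubations preceding the gas. The 21% is itself a planning assumption for 72 h, while the window runs from 64 h to 80 h, so the number concerned could be lower or higher. The documents do not allow the effect in this trial to be computed, and the planned 28 per arm is not shown to be wrong.

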**9. Randomization: type**

Block randomization using at least two different block sizes, stratification by center.

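### No analysis model is stated for 72 h paCO2; pre-extubation paCO2 and centre should be pre-specified as covariates

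*Combined protocol and SAP*

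**What the plan says.** Section 5 (Outcomes) defines the primary outcome as "paCO 2 at 72 h (timeframe: 64 h to 80 h) after extubation". Section 6 (Sample size) sets 28 infants per arm "to detect a difference in the paCO 2 of 7 mmHg between the study groups". It takes alpha as 0.05 (two-sided) and power as 0.80, with an allowance for 21% reintubation within 72 h. No SD is printed; the section relies on earlier data from the unit: "Assuming a variability of the paCO 2 as previously reported for difficult-to-wean preterm infants in our unit".

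No section names a test, a model, an effect measure or covariates for the primary outcome. Sections 1 to 11 are numbered without a break and none covers statistical analysis, so this is not a gap left by redaction.

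Two natural covariates are already in the plan:

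- The planned data collection in section 4 (Intervention) lists "Blood gas result before extubation (pH, paO 2 , paCO 2 and BE" among its items.
- Section 9 (Randomization: type) specifies "Block randomization using at least two different block sizes, stratification by center".

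Section 7 adds an interim look: "An independent statistician performs an interim-analysis on the primary and secondary endpoints once 50% of the patients are randomized". It gives no method either.

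**The concern.** The sample size sentence neither plans nor excludes adjustment. Three things follow from leaving the model open.

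- **Precision.** If 72 h paCO2 is correlated with pre-extubation paCO2, an unadjusted comparison leaves explainable variation in the standard error. In a trial of 56 infants, a chance difference between arms at baseline also passes into the estimate in proportion to the regression slope.
- **Agreement with the design.** Stratifying by centre balances the arms within centre. If centre is prognostic and the analysis ignores it, the standard error is too large and the test is conservative.
- **Freedom of choice.** The primary endpoint is analysed at half recruitment. Unless the model is fixed before then, the choice between adjusted and unadjusted results can be made with data in view.

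**Working it through.** **Inputs from the documents.** Difference 7 mmHg, two-sided alpha 0.05, power 0.80, 28 per arm, 21% reintubation (section 6); two centres (section 3).

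**Assumptions not in the documents.** The correlation r between pre-extubation and 72 h paCO2; the SD, which has to be back-solved; and that the 21% is a loss allowance.

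**The plan's own figure.** 28 × (1 − 0.21) = 22.1, so about 22 evaluable per arm. With a two-sample t-test on 2 × 22 − 2 = 42 degrees of freedom (noncentral t), power 0.80 needs a standardised difference of 0.865, so SD = 7 / 0.865 = 8.1 mmHg. If all 28 per arm are evaluable, the standardised difference is 0.762 and SD = 7 / 0.762 = 9.18 mmHg. The stated 28 is therefore attainable, but it cannot be confirmed without the SD.

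**Adjusted analysis.** Fitting arm, baseline paCO2 and centre leaves 44 − 4 = 40 degrees of freedom. The variance of the treatment estimate is multiplied by (1 − r²)(1 + 1/39). The second factor is the cost of estimating the baseline slope. No centre effect is assumed, so centre brings only its cost. With 28 per arm there are 52 degrees of freedom and the second factor is 1 + 1/51. CI half-widths are simulation means (60,000 trials per r, two equal centres).

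| r | Power, 22 per arm | Mean 95% CI half-width, 22 per arm (mmHg) | Power, 28 per arm |
|---|---|---|---|
| Unadjusted | 0.800 | 4.90 | 0.800 |
| 0 | 0.789 | 4.96 | 0.792 |
| 0.2 | 0.805 | 4.86 | 0.808 |
| 0.3 | 0.825 | 4.74 | 0.828 |
| 0.4 | 0.854 | 4.55 | 0.857 |
| 0.5 | 0.891 | 4.30 | 0.893 |
| 0.6 | 0.932 | 3.97 | 0.934 |

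Adjusted power equals 0.80 at r = 0.165 with 22 per arm and at r = 0.144 with 28 per arm.

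**Baseline imbalance.** A one-standard-error difference between arms in baseline paCO2 shifts the unadjusted estimate by r × SD × √(2/n). With 22 per arm, 8.1 × √(2/22) = 2.44 mmHg. The shift is 0.3 × 2.44 = 0.73 mmHg at r = 0.3 and 0.5 × 2.44 = 1.22 mmHg at r = 0.5.

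**Centre.** The documents give no centre effect, so its share of the paCO2 variance was assumed. In 20,000 simulated trials (22 per arm, balanced within two equal centres), a t-test ignoring centre had type I error of 0.050, 0.039 and 0.029 when centre explained 0%, 10% and 20% of the variance. In a separate simulation of 4,000 trials per setting, the model with baseline and centre stayed near 0.05.

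**The case against.** The missing model is a fact, but the choice of covariates is a recommendation. An unadjusted comparison is valid, and pre-specifying one would also remove the risk of choosing after the results are seen.

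The gain cannot be known from the documents: SD, r and the centre effect are all absent. There is reason to expect a modest r. Entry requires "paCO 2 <65 mmHg with pH >7.2", which truncates the baseline range. Baseline is taken on invasive ventilation, while the outcome comes 64 to 80 h after extubation, with weaning and escalation at the physician's discretion. At r = 0.2 adjustment adds half a point of power and narrows the CI half-width by 0.04 mmHg. The larger gains need r of 0.5 or more, which nothing in the documents supports. The pre-extubation gas also has no stated time window.

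Finally, a covariate set does not say how reintubated or rescued infants are analysed, which may matter more.

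Most of this stands as a limit on the size of the benefit. It does not remove the point. The model is absent whatever r is, and adjustment costs about 1 point of power at worst. Centre is the stratification factor, so including it makes the standard error match the design. The handling of reintubated and rescued infants is a separate gap that also has to be closed.

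**Conclusion.** The concern holds. The plan states no primary analysis model and leaves unused a baseline value that it collects and the one factor by which it stratifies. The model should be fixed; an unadjusted analysis would not be wrong.

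The size of the benefit is uncertain. Below r of about 0.17, adjustment costs at most about 1 point of power. Above that it gains: about 2.5 points at r = 0.3 and 9 points at r = 0.5. These figures assume 22 evaluable per arm, unadjusted power of exactly 0.80 and no centre effect. With 28 evaluable per arm they hardly change. No numerical gain is claimed for centre, because the documents give nothing from which to calculate one. Confidence is medium, since r is unknown and could be low.

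**What to change.** Before the interim analysis, add an analysis statement: a linear model of 72 h paCO2 on randomised arm, adjusted for pre-extubation paCO2 and centre, reporting the adjusted mean difference with its 95% CI. The statement should also say which pre-extubation blood gas is the baseline value.

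For consistency, the other post-extubation blood-gas outcomes (pH, paO2, paCO2 and BE at 2 h; pH, paO2 and BE at 72 h) can use the same model with the matching pre-extubation value. No gain is claimed for these.

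The cost is one or two sentences. The data are already planned and no infants are added. Residual degrees of freedom fall from 42 to 40 with 22 per arm, which lowers power from 0.80 to 0.79 if r = 0.
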